5.8 Data collection if patient unable to attend visits

There may be situations where a patient is unable to attend for study visits, for example due to needing to isolate because of COVID-19. Wherever possible, this should be rearranged to another time within the visit window (please see section 5.4.1 Schedule of Events for details regarding visit windows). If this is not possible then the visit should be arranged to take place remotely with as many procedures completed as possible. This should include spirometry where the patient has access to suitable equipment at home and is required for a study visit. Home recorded FEV1 and FVC values should not be used as definitive readings for classifying non-responders.

The week 12 assessment of response visit must take place in clinic and cannot be completed remotely. If a patient is unable to attend a planned week 12 visit then it should be rearranged to another time within the visit window. If this is not possible then it should take place as soon as possible outside the window and reported as a deviation.

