3.3 Flow Charts of Study Design and Research Activity

3.3.1 Overview of Study Design

3.3.2 Flow Chart of Research Activity

3.4 Primary and secondary outcome measures/endpoints

3.4.1 Primary outcome measure

Lung function stabilisation will be derived from change in FEV1 and FVC at 12 and 24 weeks compared to baseline at study entry. At baseline and 24 weeks FEV1 and FVC will be taken from Full Pulmonary Function Tests (PFT) carried out as a research assessment. At 12 weeks FEV1 and FVC values will be taken from those collected as part of routine clinical assessment.

Full Pulmonary Function Tests

Full pulmonary function tests to include FEV1, FVC, FEF25-75, Flow-volume loop, TLC, RV, Va, TLCO and KCO should be performed in a fully accredited lung function laboratory by or under the close supervision of a qualified pulmonary physiologist. Results should be provided as absolute values, % predicted values and z-scores. All spirometry should be performed according to ATS/ERS standards. If a bronchodilator response is performed, then post-bronchodilator FEV1 and FVC values should be reported.

Routine spirometry tests

Routine clinic spirometry as collected regularly in the transplant clinic should be performed in accordance with usual clinical practice in the transplant centre by a trained individual able to ensure adequate reproducibility/quality control of the test and reporting of absolute values of FEV1 and FVC. Tests can be performed in either an accredited lung function laboratory or using a desktop or handheld spirometer as long as adequately supervised. Interpretation of the routine spirometry will be by the participant's lung transplant physician. Home spirometry results performed by participants using a handheld spirometer already in their possession can be used in place of routine clinic spirometry if it is not possible for the participant to attend. In such cases the principal investigator must be confident the participant is trained in its use and able to perform reproducible spirometry. Home spirometry cannot be used to replace the baseline and end of study full pulmonary function tests or the 12-week assessment time point.

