5.4 Follow up assessments and Data Collection

5.4.1 Schedule of Events

Activity	Screening at clinical assessments	Week 0**		Week 2 +/- 7 days	Week 4 +/- 7 days	Week 6 +/- 7 days	Week 8 +/- 7 days	Week 10 +/- 7 days	Week 12 +/- 7 days	Week 16 +/- 7 days	Week 20 +/- 7 days	Week 24 +/- 7 days ****
		Baseline Visit	ECP only* (0-14 days)	ECP only	Research Assessment	ECP only	Research Assessment	ECP only	Research Assessment	Research Assessment	Research Assessment	Research Assessment
Screening												
Screen medical notes	x											
Provide PIS	x											
Initial Eligibility check	x											
Consent												
Informed Consent		x										
Confirmation of eligibility		x										
Pregnancy Test		x										
Randomisation		x										
Safety Bloods (FBC, U&E, LFT)		x										
Routine Data Collection												
Demographics		x										
PMH		x										
Clinical/physical assessment		x			x		X		x	x	x	x
Routine blood tests***					x		X		x	x	x	x
Chest X-ray findings		x			x		X		x	x	x	x
Medication review		x			x		X		x	x	x	x
PFT Spirometry (FEV/FVC)		x			x		x		x	x	x	x
Survival status												x
Research assessments												
Research Bloods		x							x			x
6 MWT		x										x
EQ-5D-5L		x										x
SF-36 v2		x										x
ISHLT CLAD score		x										x
Research full PFT		x										x
AE & SAE Reporting			x	x	x	x	x	x	x	x	x	x
Assessment of Response									X*****			
Assess if cannula possible or catheter required		x										
ECP arm only												
ECP Cycle (2 days) + clinical bloods			1	2	3	4	5	6	7	8	9	
∞Pre and post ECP (NCL only) (2 x 20mls)			x						x		x	
*The first ECP cycle should ideally take place within 14 days of randomisation. If ECP cycle 1 is >28 days after randomisation this should be documented as a deviation If ECP cycle 1 is >14 days after randomisation then baseline Spirometry should be repeated ****Visit window extended to +30 days if participant believed to have treatable non-CLAD condition at time of planned visit					**Follow up assessments are from date of randomisation in control arm, and from date of commencing ECP for intervention arm. *** Routine Blood Tests – Full Blood Count, Urea and Electrolytes and Liver Function tests ***** For those in the ECP arm participants must have received 6 treatment cycles prior to the formal 12 week assessment of response taking place – see sections 5.4.5 and 5.5.1 for details ∞ Pre and Post ECP research Blood for apoptosis assay in Newcastle participants only for mechanistic sub study							

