5.6 Final Assessment for all participants

Routine clinical data should be assessed prior to commencing research specific assessments at the final assessment schedule for week 24. If the participant has seen a drop in lung function that is believed to be non-CLAD related and reversible, then the final assessment should be rearranged to allow any treatment to take place. The rearranged visit can be up to, but no later than, 30 days after the 24 week date. Unless cancelled for non-CLAD reasons as outlined above, the week 24 visit should take place at 24 weeks +/- 7 days.

The following research specific assessments will be repeated at the final assessment at 24 weeks:

- Full Pulmonary Function Tests (PFT):
 - Spirometry comprising FEV1 and FVC.
 - Flow Volume Loop including FEF25-75
 - Static Lung volumes comprising Total Lung Capacity (TLC) and Residual Volume (RV).
 - Total diffusing capacity (DLCO), alveolar volume (Va) and volume corrected diffusing capacity (KCO).
 - Pulse oximetry at rest.
- 6 MWT
- EQ-5D-5L questionnaire
- SF-36 v2 questionnaire

Where a participant is withdrawn from the study before the final assessment, the final assessment should be carried out as close to the time of withdrawal with the participant's permission.

See withdrawal section 5.12 for further details.

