7.3 Lung Function

Lung function stabilisation – defined as a less than or equal to a 10% loss in FEV1 and FVC from study baseline to 24 weeks.

Rapid decline – defined as a greater than 20% fall in FEV1 or FVC in the first 12 weeks from study baseline.

Non-responders – As outlined in the study flow chart in Section 3.3, a non-responder is defined as someone who experiences a decline in FEV1 or FVC of more than 10% at 24 weeks compared to baseline readings due to progressive CLAD. A non-responder may also be someone with a decline in FEV1 or FVC of >20% within 12 weeks of the baseline visit that is confirmed as being due to progressive CLAD.

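### Section 5.8 directs a missed week-24 visit to a remote visit that cannot supply the primary-endpoint lung function, and gives only week 12 a late in-clinic route

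*Protocol*

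**What the plan says.** **Missed visits (Protocol 5.8).** A visit that cannot be attended is first rearranged within its window. Failing that: "If this is not possible then the visit should be arranged to take place remotely with as many procedures completed as possible". Home spirometry is included where the participant has equipment, but "Home recorded FEV1 and FVC values should not be used as definitive readings for classifying non-responders". Week 12 is the one exception. It must be held in clinic, and when the window cannot be met: "If this is not possible then it should take place as soon as possible outside the window and reported as a deviation".

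**Source of the 24-week value (3.4.1).** "At baseline and 24 weeks FEV1 and FVC will be taken from Full Pulmonary Function Tests (PFT) carried out as a research assessment". Further, "Home spirometry cannot be used to replace the baseline and end of study full pulmonary function tests or the 12-week assessment time point".

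**Use of the value (7.3).** Lung function stabilisation is "defined as a less than or equal to a 10% loss in FEV1 and FVC from study baseline to 24 weeks". The same section defines a non-responder partly by a decline of more than 10% at 24 weeks, so the bar on home readings in 5.8 reaches week 24 as well as week 12.

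**Timing of week 24 (5.6 and 5.4.1).** A drop believed to be reversible and unrelated to CLAD allows the final assessment to move, to no later than 30 days after the 24-week date. Otherwise: "Unless cancelled for non-CLAD reasons as outlined above, the week 24 visit should take place at 24 weeks +/- 7 days". The Schedule of Events footnote reads: "Visit window extended to +30 days if participant believed to have treatable non-CLAD condition at time of planned visit".

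**The concern.** Each rule is reasonable alone, but together they leave a gap at week 24. A participant who cannot reach the hospital within the 15-day window, for a reason that is not a treatable non-CLAD condition, is directed to a remote visit. The only lung function obtainable there is home spirometry, which the protocol does not accept for this time point. The same participant at week 12 would be seen in clinic a little late and would keep a usable value.

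At stake is the 24-week half of the primary endpoint. The loss would be avoidable, because a PFT shortly after the window would usually be informative. It could also be informative missingness: the extension excludes absence caused by CLAD itself, so some of those left without a route may be deteriorating. Five centres in an open-label trial could also resolve the gap differently.

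**Working it through.** **1. The rules side by side**

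| Reason the window is missed | 30-day extension? | What the text directs | Usable 24-week FEV1/FVC? |
|---|---|---|---|
| Reversible non-CLAD drop in lung function | Yes (5.6) | Late final assessment | Yes |
| Treatable non-CLAD condition, with or without a drop | Yes (Schedule footnote) | Late final assessment | Yes |
| Logistics, or isolation without a treatable condition | No | Remote visit (5.8) | No (3.4.1, 5.8) |
| CLAD-related inability to travel | No | Remote visit (5.8) | No (3.4.1, 5.8) |

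At week 12 the last two rows would lead to a late in-clinic visit, reported as a deviation.

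**2. The plan's own power (10.1)**

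Inputs: 45 per arm, 30% v 55%, one-sided 5%, stated power 80% with Barnard's test.

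- Unpooled normal approximation: standard error = √[(0.30×0.70 + 0.55×0.45)/45] = 0.1008; 0.25/0.1008 − 1.645 = 0.83; power 79.8%.
- Pooled null variance: null standard error = √[2×0.425×0.575/45] = 0.1042; (0.25 − 1.645×0.1042)/0.1008 = 0.78; power 78.2%.
- Barnard's test ordered by the z statistic: 76.9%.

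The approximations reproduce the stated figure to within 2 points, and the exact test to within about 3. Nothing below depends on that gap.

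**3. Power if values are lost**

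The protocol gives no rate of missed week-24 visits, so the counts are assumptions.

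| Values lost of 90 | Share | Per arm left | Pooled z power |
|---|---|---|---|
| 0 | 0% | 45 | 78.2% |
| 3 | 3.3% | 43.5 | 77.0% |
| 5 | 5.6% | 42.5 | 76.1% |
| 9 | 10% | 40.5 | 74.3% |

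Barnard's test gives 76.1% at 43 per arm and 72.3% at 40. None of these figures is the power of the planned augmented binary analysis; they show only the order of the loss.

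**4. Bias in a complete-case comparison if the lost participants are all true failures**

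Expected responders are 0.30×45 = 13.5 (SOC) and 0.55×45 = 24.75 (ECP).

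- 4 lost in SOC, 2 in ECP: 24.75/43 − 13.5/41 = 57.6% − 32.9% = 24.6 points (from unrounded rates), against 25.0.
- 4 lost in SOC only: 55.0% − 32.9% = 22.1 points.
- 4 lost in ECP only: 24.75/41 − 30.0% = 60.4% − 30.0% = 30.4 points.

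Bounds with 4 values missing in each arm and observed rates of 30% and 55% among the other 41:

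- Lowest: (22.55 − 16.3)/45 = 13.9 points.
- Highest: (26.55 − 12.3)/45 = 31.7 points.

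**5. Price of a late reading**

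If loss is assumed steady at 10% per 24 weeks (168 days), a reading 30 days late adds 10 × 30/168 = 1.8 percentage points of decline.

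**The case against.** The strongest reply is that this is a missing clarification, not a rule that destroys data. That is largely right. A reader might infer that the protocol forbids a late PFT or discards its result. It does neither. The wording in 5.6 and 5.8 is advisory, deviations are logged (13.5), and a remote visit does not formally waive the outstanding PFT. What stands is that the stated direction is a remote visit, while the late in-clinic route is written for week 12 only.

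Other points on that side:

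- **The extension is wide.** The Schedule footnote needs no fall in lung function, so many infections and intercurrent admissions qualify. The remainder is narrower: CLAD-related inability to travel, logistics, and isolation without a treatable condition.
- **The sickest are partly covered.** Rapid decliners confirmed by week 12 count as non-stabilised (5.5.3). Participants who withdraw should, with permission, have the final assessment close to withdrawal (5.6, 5.12). It is tempting to say that losses will fall mainly on the sickest; the documents do not say so, and it remains an inference.
- **The analysis is not a simple count.** The joint model in 10.3.1 uses 12-week and 24-week changes, so it would be wrong to say that someone without a 24-week value contributes nothing. Section 10.3.5 plans to examine missingness and to consider imputation at roughly more than 10% missing. The counts assumed above reach but do not exceed that level. Neither device removes bias if missingness depends on decline after week 12.
- **Week 12 has its own reason for an exemption.** It precedes the decision on the seventh ECP cycle (5.4.5). Response requires both time points, so nothing supports calling week 12 the less critical one.
- **The losses fit the allowance.** Section 10.1 allows 10% dropout and puts the maximum needed for 80% power in the augmented binary analysis at 68. This answers the power question, not the bias question.

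**Conclusion.** The point holds in a limited form. Followed as written, sections 5.8, 3.4.1 and 5.6 direct some participants to a week-24 visit that cannot yield the primary measurement, when a slightly late PFT could.

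The expected loss of power is small: about 1 to 4 points for 3 to 9 lost values. Losses of failures spread across both arms barely move the estimated difference. Shifts of about 3 to 5 points need four failures lost from one arm only, and the documents give no mechanism that would make that likely. All these sizes rest on assumed loss counts and on simple two-proportion calculations, not on the planned joint model. The case for acting is that the loss is avoidable, concerns the primary endpoint, and is cheap to prevent.

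**What to change.** - **Section 5.8:** extend the week-12 exception to week 24. Suggested sense: *weeks 12 and 24 are held in person; if a participant cannot attend week 24 within the window, the full PFT is done at the earliest opportunity afterwards, at most 30 days after the 24-week date, and logged as a deviation.*
- **Section 5.6 and the Schedule of Events footnote:** align the ±7-day sentence and the extension with this.
- **Analysis:** use that FEV1 and FVC as the 24-week value, record the actual date, and repeat the primary analysis without out-of-window values as a sensitivity analysis. That detail can sit in the SAP.
- **Do not** accept routine clinic spirometry as the primary 24-week value. It would change the source set in 3.4.1; at most it belongs in a sensitivity analysis.

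The cost is a few sentences and a footnote. A few readings would be up to 30 days late, adding about 1.8 points of decline under the assumption above. That could reclassify someone close to the 10% limit, which is why the sensitivity analysis is needed. Anyone already seen remotely would need a further in-person visit.

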5.10 Payments to Participants

The research team at each site will support lung transplant recipients taking part in the study. All the participants will be well known to their local clinical team, the site PI, and most Co-Investigators as they will be under regular follow up at the centre. No payments or rewards are being provided to patients for participating in the trial itself, but the trial will provide an allowance for expenses associated with participation. Due to the intensive schedule of visits, especially in the ECP treatment arm, and the distances that many lung transplant recipients live from their transplant centre, we will support a contribution to travel and accommodation costs for them and an accompanying carer where appropriate. A tailored approach to travel and accommodation support will be taken, depending on travel distances and ease of commuting and if they have their own transport available which is a preferred route for most to attend for treatment. Costs will only be provided as part of the study when the visit is entirely study related as several of the study activities will coincide with scheduled clinic visits, which the patients would be making anyway.

5.11 Discontinuation of Allocated Trial Treatment

Participants have the right to discontinue their allocated trial treatment at any time. The participant is not required to provide a reason; however, they will be encouraged to do so to ensure that information relevant to the trial design, medication / intervention tolerability and efficacy is collected where possible. A Discontinuation of Trial Treatment Form needs to be completed and any reason provided should be documented in both the electronic case report form (eCRF) and the participant's medical records.

All participants choosing to discontinue ECP treatment / SOC treatment for reasons other than disease progression (for example personal choice) should be encouraged to continue with the remaining trial visits and assessments. The investigator/treating clinician will discuss with the participant which remaining trial visits are required and if the participant finds this acceptable to continue with the visits.

Following cessation of ECP treatment / SOC treatment, the participant's treatment regimen will be decided by the investigator/treating clinician as per routine care.

Please note: If the participant starts another rescue therapy that is not part of usual standard of care (for example TLI) they will then need to be withdrawn from the trial and no further trial visits will occur once this rescue therapy has started, however the patient will be asked to allow the use of routinely collected data until the end of the trial follow up period.

5.12 Withdrawal from Trial

Either the participant or the treating clinician may make the decision to withdraw the patient from the trial. Discontinuation of allocated trial ECP treatment or SOC treatment is not necessarily a withdrawal from the trial if the participant is willing to continue with trial visits where this is an option (see section 5.11). **Please note:** where trial treatment is being stopped due to non-response and need for rescue treatment, the participant must be fully withdrawn from the trial. Please see appendix 5 for non-responder decision tree.

If the participant is withdrawn from the trial, they cannot continue with ECP treatment and will be followed up for adverse event reporting purposes only for an additional 4 weeks from the point of stopping ECP. With participant consent, the week 24 research activities (see section 5.6) should be undertaken at the last study visit before withdrawal. If the participant is withdrawn after the baseline visit and before the week 12 visit then, with consent, the week 12 research blood samples should be collected at the last study visit before withdrawal. If the participant is withdrawn after the week 12 visit, then no further research blood samples are required.

All withdrawals from the trial should be asked if they allow the use of routinely collected data for the remainder of the trial follow up period

If the patient requests to withdraw from the mechanistic sub-study or qualitative sub-study, they can still remain in the main trial.

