2.2 Secondary Objectives

To determine how the treatment strategies of ECP therapy plus SOC and SOC alone affect the following outcomes over a 24-week period:

- Change in rate of decline in lung allograft function between before randomisation (available from clinical records) and up to 24 weeks after randomisation, measured by change in FEV1 and FVC (litres/month).
- Absolute change in lung allograft dysfunction from baseline to 24 weeks, measured by FEV1 and FVC (litres).
- Change in exercise capacity from baseline to 24 weeks measured by distance walked (metres) during a 6-minute walk test.
- Change in disease severity from baseline to 24 weeks measured by ISHLT CLAD Stage (1-4).
- Change in health-related quality of life from baseline to 24 weeks measured by SF-36 v2 and EQ-5D-5L.
- Survival at 24 weeks after randomisation (end of study).
- Adverse events (AEs) and Serious adverse events (SAEs) from randomisation to 24 weeks.

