5.12.2. Investigator Led Withdrawal from the trial

The investigator/treating clinician may withdraw a participant from the trial at any time if they deem it necessary for the following reasons:

- Continuing to attend trial visits and undergoing trial assessments would place unreasonable demands on the physical or psychological health of the participant. If participant and investigator agree, any assessments occurring as part of routine care would also be recorded in the eCRF.

- The participant loses capacity for a prolonged period.
- An adverse event, which results in inability to continue to comply with trial procedures.
- Inability to secure appropriate vascular access for ECP treatment to be delivered to participant in the ECP+SOC arm.
- Pregnancy.
- Significant protocol deviation or non-compliance.
- Termination of the clinical trial by the Sponsor.

Where the decision is taken by the clinician to fully withdraw the participant from the trial, the following procedures will apply:

- If the participant has not yet received any ECP treatment, the participant should not participate in any further trial-related procedures.
- If the participant has received any ECP treatment including IMP administration as part of the process, the ECP treatment should be stopped, and followed up for adverse event reporting purposes only for an additional 4 weeks.

Information that a participant has received ECP treatment even if incorrectly enrolled/randomised must be documented in the eCRF.

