9.2 Recording and Reporting AEs and SAEs

Adverse Events:

All AEs occurring from the time of consent to end of trial participation, must be recorded in the AE eCRF page as well as the participant's medical notes.

Events which are due to the symptomatic deterioration of the participant, and which are expected for participants who have CLAD progression, do not need to be reported as AEs. These events will be recorded in the participant record and will be reported in the eCRF, but not as AEs.

All adverse events which are not associated with the deterioration of the participant or their non-response to treatment will be recorded as AEs, both for participants in the ECP treatment group and also for those in the SOC group. These events include the following:

- Transient fever
- Transient hypotension
- Dizziness / Pre-Syncope
- Nausea
- Vomiting
- Loss of appetite
- Headache
- Fatigue
- Minor photosensitivity reactions
- Local site infections associated with peripheral or central venous catheterisation
- Other Infections of all types: Bacterial Fungal Viral
- Worsening of any baseline medical condition eg hypertension, diabetes, gastro-oesophageal reflux
- Need for blood transfusion
- Need for platelet transfusion

This list is not exhaustive and any other AE which, in the opinion of the investigator is not due to the progression of CLAD, should be reported as an AE.

Serious Adverse Events and Serious Adverse Reactions:

All SAEs occurring from point of consent to end of trial participation (end of the last trial related assessment) must be reported to NCTU on an SAE form and recorded in the AE eCRF page and recorded as serious.

All SARs occurring from the time of first ECP treatment up until the last trial related assessment for the participant at week 24 must be reported to NCTU on an SAE form and also recorded in the AE eCRF page and recorded as serious. All participants in the ECP arm must be followed up for a minimum of 4 weeks after the last ECP treatment.

Following this defined active monitoring period for SARs, investigators are still required to report any SARs or SUSARs they become aware of for all trial participants for the duration of the study (i.e. up until LPLV).

An unscheduled hospitalisation, with any of the following causes, will need to be reported as an SAE:

- Systemic infection associated with central venous catheter use
- Systemic infections associated with peripheral cannulation
- Sepsis of any cause
- Pulmonary embolus

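### After withdrawal, active adverse event follow-up is specified only for participants who have received ECP, and no rule carries withdrawn participants in either arm to the 24 weeks in the safety objective

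*Protocol*

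**What the plan says.** - **Objective.** Protocol Section 2.2 lists "Adverse events (AEs) and Serious adverse events (SAEs) from randomisation to 24 weeks" among the outcomes to be compared. Section 10.2 places all recruited patients in the safety population.
- **Reporting period.** Section 9.2 covers "All AEs occurring from the time of consent to end of trial participation". For SAEs it says "All SAEs occurring from point of consent to end of trial participation (end of the last trial related assessment) must be reported".
- **What ends participation.** Sections 5.5.3, 5.11 and 5.12 require full withdrawal once rescue treatment outside standard of care begins. Section 5.11 adds that trial visits then stop.
- **After withdrawal, general rule.** Section 5.12 says the participant "will be followed up for adverse event reporting purposes only for an additional 4 weeks from the point of stopping ECP".
- **After investigator-led withdrawal.** Section 5.12.2 splits by treatment received. With any ECP, "the ECP treatment should be stopped, and followed up for adverse event reporting purposes only for an additional 4 weeks". With none, "If the participant has not yet received any ECP treatment, the participant should not participate in any further trial-related procedures".
- **ECP-arm minimum.** Section 9.2 adds "All participants in the ECP arm must be followed up for a minimum of 4 weeks after the last ECP treatment". It has no SOC counterpart.
- **Routine data.** Sections 5.11, 5.12 and 5.12.1 ask those who withdraw, in either arm, to allow use of routinely collected data to the end of the follow-up period.

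**The concern.** The objective promises a comparison over one fixed window, but the collection rules do not deliver that window for anyone who withdraws. A withdrawn SOC participant has no active AE follow-up specified. A withdrawn, treated ECP participant has up to four more weeks. Neither is carried to week 24.

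Withdrawal is also linked to outcome. Section 8.1 makes a fall of more than 20% in lung function the gateway to rescue, so collection stops first in the participants who are doing worst. Section 10.1 assumes 30% responders in SOC and 55% with ECP, which makes more exits from SOC plausible, although a non-responder does not have to leave.

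Rescue therapy adds a further imbalance. Section 5.5.1 suggests preparing rescue so that it can start soon after the week 12 visit. Events under rescue can then fall inside the four weeks recorded for an ECP leaver. The same kind of event in a SOC leaver, who under Appendix 1 may be considered for TLI or ECP, falls after active collection has ended.

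**Working it through.** The protocol states no figure for the length of safety follow-up achieved, so there is none to reproduce. The check sets the rules side by side and then illustrates the size.

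**1. Active AE follow-up stated after withdrawal**

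| Withdrawn participant | Stated follow-up |
|---|---|
| ECP arm, treated | Four weeks from stopping ECP (5.12); four weeks, starting point not given (5.12.2) |
| ECP arm, never treated | None; no further trial procedures after investigator-led withdrawal (5.12.2) |
| SOC | None |
| Anyone giving permission | Routine data to the end of follow-up, not tied to AE or SAE reporting |

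Section 9.2 keeps a duty to report later SARs and SUSARs that investigators become aware of. That duty does not cover SAEs in general, so it does not fill the SOC gap.

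**2. Time gained from the four-week clause**

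Section 5.4.5 requires the week 12 decision before cycle 7, so the last scheduled ECP before it is cycle 6, at week 10.
- Counted from the last treatment: 10 + 4 = week 14, a gain of 2 weeks for someone leaving at week 12.
- Counted from the week 12 decision: 12 + 4 = week 16, a gain of 4 weeks.
- Leaving at week 16 before cycle 8, last treated at week 12: 12 + 4 = week 16, a gain of 0.

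The gain is therefore 0 to 4 weeks.

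**3. Mean collection window per arm**

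Mean window = 24 − w × (24 − min(24, t + g)), where w is the share withdrawn, t the week of withdrawal and g the weeks gained (0 in SOC). The values of w and t are assumptions.

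| Withdrawn at week 12 | SOC (weeks) | ECP, g = 2 (ratio) | ECP, g = 4 (ratio) |
|---|---|---|---|
| 10% in each arm | 22.8 | 23.0 (1.009) | 23.2 (1.018) |
| 20% in each arm | 21.6 | 22.0 (1.019) | 22.4 (1.037) |
| 30% in each arm | 20.4 | 21.0 (1.029) | 21.6 (1.059) |
| 30% SOC, 15% ECP | 20.4 | 22.5 (1.103) | 22.8 (1.118) |
| 40% SOC, 20% ECP | 19.2 | 22.0 (1.146) | 22.4 (1.167) |

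Example, last row: SOC 24 − 0.40 × 12 = 19.2; ECP with g = 4, 24 − 0.20 × 8 = 22.4; 22.4 / 19.2 = 1.167.

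**4. Source of the gap in the last row**

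Without the clause the ECP window is 24 − 0.20 × 12 = 21.6, already 21.6 / 19.2 = 1.125 times the SOC window. Of the total gap of 22.4 − 19.2 = 3.2 weeks, 21.6 − 19.2 = 2.4 weeks come from stopping collection at withdrawal. The clause adds 22.4 − 21.6 = 0.8.

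**5. Effect of a remedy**

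Giving SOC leavers the same four weeks from week 12 gives 24 − 0.40 × 8 = 20.8 weeks, and 22.4 / 20.8 = 1.077, so a gap remains. Collecting to week 24 for everyone gives 24 weeks in both arms, a ratio of 1.00.

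The illustration starts both arms at the same week 0. Section 5.4.1 in fact starts the clock at randomisation in SOC and at first ECP in the ECP arm. That is a separate difference and is not counted here.

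**The case against.** The strongest reply has four parts.

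- **The clause is a safety minimum.** Four weeks of follow-up after ECP is ordinary for an investigational product, and its purpose is not to compare arms. That stands, and the clause should be kept.
- **Routine data are sought in both arms.** Under Section 5.4.3 they include hospital admissions and unscheduled visits, which could reveal many SAEs. A reader might infer from Section 5.12 that nothing at all is collected from SOC after withdrawal. The documents do not support that. What remains is that this route is passive, needs permission and is not connected to AE or SAE reporting.
- **The analysis is not fixed here.** Section 10 defers it to a SAP that is not at hand, and rates per patient-week would largely remove the difference in length. That stands as far as length goes. Rates cannot recover events that were never collected, nor correct for collection that stops because the participant is deteriorating.
- **The loss is limited.** Section 9.2 does not count expected events of CLAD progression as AEs. Survival at 24 weeks is a separate outcome with its own status item in Section 5.4.1. A participant who stops treatment without withdrawing is encouraged to keep attending (Section 5.11). Non-responders may also stay in the trial. All of this stands and narrows the point to AEs and SAEs in those who fully withdraw.

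A reader might also infer that an ECP participant leaving at week 12 always has 16 weeks of collection against 12 in SOC. Section 5.12 counts from stopping ECP, so week 14 is equally possible, and a later leaver may gain nothing.

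**Conclusion.** The concern holds in a limited form. For participants who withdraw, the collection rules do not deliver the 24-week window in the objective. The only active follow-up specified after withdrawal depends on having received ECP. The comparison of AEs and SAEs is open to bias from unequal, outcome-related ascertainment.

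The size cannot be fixed from the protocol, because it gives no exit rates by arm. Under equal exits of 10% to 30% at week 12, the mean window is about 1% to 6% longer with ECP. Under 40% SOC and 20% ECP exits it is up to about 17% longer, and about three quarters of that gap (2.4 of 3.2 weeks) comes from stopping collection at withdrawal.

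It is tempting to conclude that the safety comparison is biased and that ECP will look more harmful than it is. The documents do not establish that. Raw counts would tend that way if more SOC participants leave, but neither the exit rates nor the summary measure is known.

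**What to change.** In Sections 5.12, 5.12.2 and 9.2, state one rule for both arms:

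- Collect SAEs, and AEs where obtainable, to 24 weeks after randomisation for every randomised participant who has not refused, whether or not ECP was received.
- Use the routine-data permission already sought, or a telephone check, and say that what is found is entered as AE or SAE data.
- Record the date on which any rescue therapy starts, so that later events can be identified.
- Keep the four weeks after the last ECP as a minimum safety requirement, and compare the arms over the common window from randomisation.

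The cost is protocol wording, a few calls or record checks, and slightly more SAE reporting for withdrawn participants. No treatment or rescue rule changes.
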